### **Candidates with an undiagnosed suspicious lesion:**

- It is not typically readily apparent from a patient's medical record how suspicious their oral/oropharyngeal lesion is. These patients will not be approached about the study in advance of their clinic visit, instead, the patient's clinical care team will be alerted that the patient may be a candidate. If, upon visual inspection by the care team, the lesion does appear to be a squamous cell carcinoma and a diagnostic biopsy is indicated, the clinical care team will be asked, upon assent of the patient, to notify a member of the study team to present the study prior to the collection of the biopsy.

Recruitment efforts will be documented on the NCI Division of Cancer Prevention's Accrual Quality Improvement Program (AQuIP) website. An entry will be made for each clinic patient who meets the primary eligibility criterion for the study (i.e. each patient with a newly diagnosed, histologically confirmed, stage 0-IV squamous cell carcinoma of the oral cavity or oropharynx who will be undergoing definitive surgical, radiotherapy, or chemoradiation treatment or with a lesion in the oral cavity or oropharynx that is not yet biopsied but is highly suspicious for cancer. AQuIP data is submitted monthly by the CLO. Participating organizations must have their monthly data entered prior to the 5th of the following month (i.e. January data must be entered by February 5th).

Patients diagnosed with, or suspected of having, oral or oropharynx cancers are highly motivated to explore prevention options. Because patients often travel some distance for treatment at these centers, the baseline visit and randomization process has been streamlined so that all procedures can be completed in a single visit if need be. An interim phone contact will be made in lieu of an additional study visit. Participants will be offered adequate remuneration to cover their travel costs. Participants who had a standard of care staging PET/CT prior to starting study intervention and are scheduled for an end of study follow-up PET/CT will be reimbursed for overnight accommodations if the PET/CT is unable to be scheduled on the same day as the rest of their end of study procedures and they travel from a distance. The protocol intervention is very short term with minimal study visits so we do not anticipate participant retention will be an issue.

## **5. AGENT ADMINISTRATION**

Intervention will be administered on an outpatient basis. Reported AEs and potential risks are described in Section 6.2.

### **5.1 Dose Regimen and Dose Groups**

Participants will be randomized in a 2:1(active agent: placebo) ratio to one of the two following treatment groups:

- Group 1: ACTOplus met® XR (30 mg pioglitazone/1000 mg metformin HCl):
  - One (1) tablet, taken daily by mouth with a meal for 10 to 21 days.
- Group 2: Placebo:
  - One (1) tablet, taken daily by mouth with a meal for 10 to 21 days.

If the end of treatment biopsy/surgical treatment is delayed beyond Day 22, participants may continue taking study agent for a maximum of 25 days. If biopsy/surgery cannot be rescheduled on or before Day 26, the participant will be unevaluable.

## **5.2 Study Agent Administration**

- 5.2.1 Study agent will be dispensed by a pharmacist or member of the study team to be self-administered by the participant.
- 5.2.2 One bottle of study agent containing 25 tablets will be dispensed to a participant after their eligibility has been confirmed by the CLO and they are randomized.
- 5.2.3 The participant will be instructed to take one (1) tablet of study agent by mouth daily with a meal at about the same time each day. The tablet must be taken whole and should not be chewed, cut, opened or crushed.
- 5.2.4 If the participant is having an end of study follow-up PET-CT scan, they should be instructed to take their dose of agent with the last full meal allowed prior to the scan.
- 5.2.5 The final dose of study agent will be taken on the day prior to the participant's day 11-22 surgery or pre-non-surgical treatment biopsy.

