### 5.7.2.1 Pill Diary (Appendix B):

Upon randomization, participants will be provided with, and instructed on the use of, a pill diary. Participants will document daily dosing of the study agent on the pill diary, noting the date and time of day that the agent was taken. A "comments" column will be included in the table for participants to make a note of any missed doses, symptoms or adverse events they experience, as well as any changes to their concomitant medications. The pill diary will also include dosing instructions and important reminders about taking the study agent. Participants will be instructed to return the Pill Diary at their end of study visit. The study coordinator or designee will review the Pill Diary with the participant and both the reviewer and the participant will sign a verification of review of the Pill Diary.

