#### 5.7.2.2 Pill count:

**Note: Due to a size discrepancy between the placebo and the active study agent, in order to preserve the study blind, pill counts should not be performed by a member of the study team. The count of returned tablets should be performed by the pharmacy or by an independent third party and reported to a member of the study team for documentation in the Visit Guide and compliance calculation.**

Each participant will be provided with a single bottle of study agent containing 25 doses of study agent. Participants will be instructed to bring this study agent bottle and any unused tablets back with them to their end of study visit. The number of returned doses of study agent will be subtracted from the number of doses dispensed to calculate the number of tablets that were taken during the dosing period (Day 1 – end of study dose). This number will be divided by the number of doses of study agent expected to be taken had the participant taken the study agent daily as prescribed. The resulting number x 100 will equal the % compliance.

$$\# \text{ of tablets taken} \div \# \text{ tablets prescribed for the dosing period} = \underline{\quad} \times 100 = \% \text{ compliance}$$

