## **7. CLINICAL EVALUATIONS AND PROCEDURES**

### **7.1 Schedule of Events**

Evaluation/ Procedure	Registration	Screening /Baseline Visit 	Randomization	Day 1	Day 5-7 Interim Phone Contact	Final Dose Reminder Call 12-72 hrs. prior to final dose time	End of Study (Day 11-22  ) or Early Termination
Informed Consent	X						
Assess Eligibility		X					
Medical/Surgical History		X					
Baseline Symptom Assessment		X					
ECOG performance status		X					
Physical Exam		X					X
Height		X					
Weight		X					X
Vital Signs (T,P,R, BP)		X					X
Clinical Safety/ Eligibility Laboratory Tests (CBC with differential, CMP, Urine Pregnancy Test  )		X					X
Blood for Pioglitazone Analysis		X					X
Tobacco and Alcohol Use Assessment		X					X
Biopsies for Tissue Biomarkers 		X 					X 
Concomitant Medications		X			X		X
Adverse Events					X		X
Dispense Study Agent			X				
Dose Study Agent				X 		X 	
Collect Study Agent							X
Review Agent Diary/Record			X				X
FDG-PET/CT scan 							X
Telephone Contact					X 	X 	

1. Within 30 days prior to Day 1 of study agent dosing.
2. May be extended up to Day 26 if participant is scheduled for surgical excision of their cancer and surgery is delayed.
3. For women of childbearing potential only.
4. Tissue Biomarkers: Tumor and normal appearing tissue samples: Proliferation index: Ki-67 expression and Cleaved Caspase 3 Immunohistochemical analyses (tumor tissue only): Cyclin D1 (ISO83), p21 (P21 Waf1/Cip1), p AKT, p AMPK, p s6, PPARγ, PD1, PD-L1, T helper (CD4), T suppressor (CD8), Fox p3 (TREG), Tumor Associated Macrophage (CD68), and p16. (HPV testing via p16 will be performed only on the baseline sample.)
5. Biopsy(baseline): 4 mm biopsy of lesion and adjacent visually normal appearing tissue
6. End of study surgery or biopsy: If participant is having a resection, collect a 4 mm biopsy of the visually normal appearing tissue adjacent to the tumor and 2 mm of tissue from the tumor. If participant will NOT be having surgical treatment, collect a 4 mm biopsy of tumor tissue as well as a 4 mm biopsy of the adjacent visually normal appearing tissue in clinic.
7. The date the first dose of study agent is taken is considered Day 1.

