**PILL DIARY PAGE 2 of 3**

**DO NOT THROW AWAY YOUR PILL BOTTLE!  
BRING IT ALONG WITH THIS PILL DIARY TO YOUR NEXT STUDY VISIT.**

DAY	DATE	TIME	COMMENTS	INITIALS
1				
2				
3				
4				
5				
6				
7				
8				
9				
10				
11				
12				
13				
14				
15				
16				
17				
18				
19				

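### Does the tablet size difference leave the study team's blind exposed when bottles are dispensed or returned?

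*Combined protocol and SAP*

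**What the plan says.** Section 5.7.2.2 gives the reason for its counting rule: "Due to a size discrepancy between the placebo and the active study agent, in order to preserve the study blind". The pharmacy or an independent third party counts the returned tablets, and the team receives only the number. Section 7.2.12 repeats this, and section 13.6 restates who counts.

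On dispensing, section 5.2.1 says: "Study agent will be dispensed by a pharmacist or member of the study team to be self-administered by the participant". Section 7.2.12 also allows courier delivery. On supply, section 5.7.2.2 says: "Each participant will be provided with a single bottle of study agent containing 25 doses of study agent". Section 5.1 sets the planned course: "One (1) tablet, taken daily by mouth with a meal for 10 to 21 days".

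On return, section 5.7.2.2 says: "Participants will be instructed to bring this study agent bottle and any unused tablets back with them to their end of study visit". The schedule in section 7.1 lists "Collect Study Agent" at that visit. Under section 5.7.2.1, "The study coordinator or designee will review the Pill Diary with the participant" when the diary is handed in.

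Sections 6.1 and 6.3 describe the placebo as matching.

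**The concern.** By barring the team from counting, the sponsor accepts that sight of the tablets could break the blind. The same logic seems to apply wherever a team member holds a bottle. Section 6.4 foresees sites without an investigational pharmacy, so dispensing by the team is a real route. At the end-of-study visit the coordinator may meet the participant, the diary and a part-full bottle together. No text requires staff, for blinding reasons, to keep the bottle closed or pass it on unopened. A site that reads only section 6 would not learn that the tablets differ.

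At stake would be the blind under which the physician attributes adverse events at the Day 5-7 contact (section 7.3.1) and at the end of study (section 7.4.5). Attribution also decides part of the dose-modification table in section 5.6. Because blocks hold two active and one placebo bottle (section 13.2), anyone certain of the placebo bottle, and of where the block begins, would know the other two.

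**Working it through.** No figure in the plan is in dispute, so the check is mainly a reading of the handling steps in order.

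**1. Are there tablets to see at return?** Tablets left = 25 dispensed − doses taken.
- 21 doses taken: 25 − 21 = 4.
- 10 doses taken: 25 − 10 = 15.
- A 10-day course at the 80% compliance limit of section 5.7.1: 0.80 × 10 = 8 taken, 25 − 8 = 17.
- 25 doses, the delayed-surgery maximum: 25 − 25 = 0.

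So a returned bottle usually holds tablets.

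**2. Which steps require someone to look inside?**

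| Step | Where | Contents must be seen? |
|---|---|---|
| Dispense | 5.2.1, 5.2.2, 6.4, 6.6 | No: one pre-packed bottle of 25, identified by its printed randomization number |
| Courier | 7.2.12 | No: the bottle is shipped and receipt verified |
| Return | 5.7.2.2, 7.1, 7.2.12 | No: the bottle is collected |
| Count | 5.7.2.2, 7.2.12, 13.6 | Yes: assigned to the pharmacy or a third party |

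The safeguard sits on the one step that needs it.

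**3. Does any text keep bottles closed?** Section 5.4.8 requires tablets to be kept tightly closed in their original container. The Pill Diary in Appendix B repeats this and tells participants not to move tablets to an organizer. The reason given is moisture and light, not blinding, but in practice tablets should come back inside a closed original bottle. Section 6.7 adds light-resistant containers. Section 6.8.2 leaves requesting and dispensing to site policy, which is not among the documents.

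**4. If a tablet were seen, what could it affect?**
- Ki-67 is quantified from stained sections by image software counting pixels (section 8.1.1). The bottle plays no part in that reading.
- The last dose is taken the day before the end-of-study procedure (section 5.2.5). Recognition at an on-schedule return could therefore reach only that participant's end-of-study attribution, not dosing.
- Recognition at dispensing could reach the Day 5-7 attribution. In section 5.6 the Grade 1 row gives a single instruction for both attribution categories, and the hypoglycemia and jaundice rules do not use attribution. That leaves the higher-grade rows.
- Each path needs someone to open a bottle without a reason, to know which size is active (the documents do not say), and to be or to influence the attributing physician (not shown).

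**The case for a change.** The best case for a change is that the protocol supplies its own premise: if sight of tablets during a count threatens the blind, so does sight of them in a clinic room. Section 6.5 also asks the investigator or a designee to record quantities returned, without repeating the counting restriction. A sentence on unopened bottles would cost little.

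Part of this stands. The text has no closed-bottle rule written for blinding, and matching does not sit well with an acknowledged size difference. But section 6.5 can be met with the number the counter reports, which is how section 5.7.2.2 says the count reaches the team. Section 7.2.12 places the restriction directly after the return instruction and states its purpose, so a coordinator reading it has both a reason to leave the bottle shut and no task that needs it open. The block argument depends on a recognition rate that the documents do not give. Participants see their own tablets whatever staff are told.

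**Conclusion.** No change to the plan follows. The missing handling sentence is a gap that site staff fill sensibly: the purpose of the restriction is stated twice, no dispensing or return task requires opening a bottle, and the counter is already someone outside the study team. The word matching in sections 6.1 and 6.3 is a clerical slip; the specific statements in 5.7.2.2 and 7.2.12 tell sites what they need to know.

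No effect on the Ki-67 comparison, on adverse event attribution or on predictability of allocation is shown. The 4 to 15 leftover tablets per fully compliant participant on the planned schedule describe opportunity only. Writing the rule down would be harmless but would change no analysis or result. This conclusion assumes that staff follow the counting restriction and do not open bottles without cause. Site dispensing policies and the Visit Guides could not be checked.

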## **5.3 Run-in Procedures**

There is no run-in phase for this protocol

## **5.4 Contraindications**

- 5.4.1 Do not take on an empty stomach.
- 5.4.2 Participants should not consume excessive amounts of alcohol as this may potentiate the effect of metformin on lactate metabolism. For females, this is more than 3 drinks on any day or a total of more than seven drinks in a week. For males, it is more than 4 drinks on any day or a total of more than 14 drinks in a week.
- 5.4.3 Do not combine with any exclusionary medications listed in section 4.2.
- 5.4.4 If a dose is missed, do not make up for the dose by double dosing the following day.
- 5.4.5 Administration of iodinated contrast agent in patients taking metformin can lead to an acute decrease in renal function and lactic acidosis. Medical tests involving the use of iodinated contrast agent include CT scan, angiography, venography, cystourethrography, hysterosalpingogram, and intravenous urography.

Participants will be instructed to inform study staff prior to undergoing any imaging studies (other than an FDG PET-CT scan which does not use iodinated contrast).

Participants who have recently had a CT scan with iodinated contrast (commonly used to stage oral/oropharyngeal cancers) must not start study agent until their eGFR has been assessed/re-assessed  $\geq$  48 hours after the scan and is found to be within normal limits. If it is not within normal limits, the study agent must be held until the eGFR is found to be within normal limits.

If the participant has not completed clinical staging at the time of the screening visit and a staging scan(s) is/are planned, study agent should not be started until the participant has completed any scans that will use iodinated contrast agent, and their eGFR has been re-assessed  $\geq$  48 hours after the scan. If it is not within normal limits, the study agent must be held until the eGFR returns to normal limits

Participants will be told to notify study staff if they are scheduled for a test using contrast agent after they have started study agent. The participant will be instructed to hold their dose of study agent on the day of the test and continue to hold study agent dosing until their eGFR is reassessed  $\geq 48$  hours after the scan and is found to be within normal limits. If it is not within normal limits, the study agent must be held until the eGFR is found to be within normal limits.

Consult with the institution performing the imaging study regarding any additional precautions they have in place.

5.4.6 Temporarily discontinue if participant will be undergoing any medical procedures requiring restricted intake of food or fluids.

5.4.7 Do not open, cut, crush or chew the tablets.

5.4.8 Keep the tablets tightly closed in their original container to keep them dry and protected from light exposure.

## **5.5 Concomitant Medications**

All medications (prescription and over-the-counter), vitamin and mineral supplements, and/or herbs taken by the participant will be documented on the concomitant medication worksheet and will include: start and stop date, dose and route of administration, and indication. Medications taken for a procedure (*e.g.*, biopsy) should also be included.

Use of any exclusionary medications is prohibited while the participant is taking study agent. Participants will be instructed to inform a member of the study staff of any new medications they are prescribed while on study prior to taking the medication.

## 5.6 Dose Modification

CTCAE v4 Grade	Attribution to Study Agent	
	Unlikely/Unrelated	Possibly/Probably/Definitely Related
1	
 
No modification unless the A.E. is unacceptable to the participant or the physician feels it is in the participant's best interest medically.
 
If the A.E. may be related to dose timing, asses how the participant is dosing their study agent and if taking it at a different time of day or with a more substantial meal might help.
 
If dose modification is necessary because taking the agent with a more substantial meal did not improve the event, the participant finds it unacceptable, or the physician feels it is in the participant's best interest medically, the participant may be instructed to take the study agent every other day.
 
If none of these measures is successful and the A.E. is unacceptable to the participant or the physician feels it is in the participant's best interest medically, study agent should be discontinued. However, the participant, if willing, should still be followed per the protocol schedule of events and have all study procedures conducted.
 
	
2	
 
No modification unless the A.E. is unacceptable to the participant or the physician feels it is in the participant's best interest medically.
 
If the A.E. may be related to dose timing, asses how the participant is dosing their study agent and if taking it at a different time of day or with a more substantial meal might help.
 
If dose modification is necessary because taking the agent with a more substantial meal did not improved the event and the participant finds it unacceptable or the physician feels it is in the participant's best interest medically, the participant may be instructed to take the study agent every other day.
 
If none of these measures is successful and the A.E. is unacceptable to the participant or the physician feels it is in the participant's best interest medically, study agent should be discontinued. However, the participant, if willing, should still be followed per the protocol schedule of events and have all study procedures conducted
 
	
 
If the A.E. may be related to dose timing, asses how the participant is dosing their study agent and if taking it at a different time of day or with a more substantial meal might help.
 
If the AE is unlikely to be related to dose timing or did not respond to taking the study agent at a different time of day or with a more substantial meal, instruct the participant to hold study agent until the AE resolves to <math>\leq</math> Grade 1 then re-start on an every-other-day dosing regimen.
 
If the AE recurs, discontinue study agent and do not re-start. However, the participant, if willing, should still be followed per the protocol schedule of events and have all study procedures conducted.
 

3	Hold study agent until consulting with the protocol's medical monitor and study chair. The medical monitor and study chair will advise whether study agent may or may not be restarted and whether a dose modification is indicated.	Discontinue study agent. Do not re-start. However, the participant, if willing, should still be followed per the protocol schedule of events and have all study procedures conducted.
4		

Hypoglycemia (The symptoms include):		
Sweating, chills and clamminess	Nervousness/shakiness/anxiety	Hunger and nausea
Irritability/impatience/confusion	Weakness/fatigue	Rapid/fast heartbeat
Numbness/tingling in the lips or tongue	Blurred/impaired vision	Sleepiness
Anger/stubbornness/sadness	Lightheaded/dizziness	Headaches
Nightmares/crying out during sleep	Lack of coordination	Seizures/ Unconsciousness

If a participant reports symptoms of hypoglycemia, instruct them to have their blood glucose level checked if possible:
 
 
• If the blood glucose level is less than the lower limit of normal but <math>\geq 55</math>mg/dL (grade 1 hypoglycemia), instruct the participant to switch to every other day dosing of the study agent. If this does not alleviate the participant's symptoms, instruct the participant to stop taking the study agent.
 
• If the blood glucose level is <math><55</math>-40 mg/dL (grade 2 hypoglycemia), instruct the participant to stop taking the study agent.
 
• If the participant is unable to have their blood glucose checked, base the dose modification on the severity of their symptoms. 
 
○ If the participant is experiencing grade 1 symptoms, and taking the study agent with a more substantial meal has not improved the symptom(s), instruct the participant to switch to every other day dosing. If this does not alleviate the symptom(s), instruct the participant to stop taking the study agent.
 
○ If the participant is experiencing grade 2 symptoms, instruct the participant to stop taking the study agent.
 
 
 
		

*For immediate, short term management of hypoglycemic symptoms, instruct the participant to try one or more of the following:
 
 
• Eat a handful of raisins or candy
 
• Drink a glass of juice, milk, or a regular (non-diet) soda
 
• Eat a small snack
 
		

Jaundice: Discontinue study agent. Do not re-start. Perform liver function tests ASAP.
		

